10.6.2 Safety Analysis

Treatment duration and amount of ISIS 420915 received (including duration and amount in the parent study) will be summarized by treatment group, as well as reasons for withdrawal from ISIS 420915.

All treatment-emergent adverse events (AEs with onset after the first dose of ISIS 420915) in this study and SAEs will be summarized by the treatment group of the parent study using the MedDRATM coding system, by system organ class, preferred term, relationship to ISIS 420915, and severity. Narratives of deaths, serious adverse events, including early withdrawals from ISIS 420915 and from study due to adverse events, will also be provided.

Laboratory tests to ensure patient safety including chemistry panel, complete blood count with differential, and coagulation panel will be summarized by study visit and by the treatment of the parent study. These safety variables will also be presented as change and percent change from baseline over time after ISIS 420915 administration, as appropriate.

Vital signs, weight, and ECG measures will be summarized by treatment group of the parent study. In addition, the number of patients who experience abnormalities in clinical laboratory evaluations will be summarized by treatment group of the parent study.

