- The Immunogenicity (IM) on-study period for the OLE study spans the time the first dose of ISIS420915 in the parent study and ends on the day of the patient's last contact date within the OLE study. This period is for defining patient IM status (Details in section 3.2.1.1.6).

3.2.1.1.5 Durations of study drug exposure and total dose of ISIS 420915:

Durations of overall drug exposure (days) across both studies will be derived as the difference in
days between the date of the last dose of ISIS 420915 and Day 1 of ISIS 420915 plus one. For
patients who are not enrolled in the OLE study, the last dose of ISIS 420915 is administered in the
parent study; for patients who are enrolled in the OLE study, the last dose of ISIS 420915 is
administered in the OLE study.

The total dose of study drug during the treatment period for either the parent study or the OLE study will be computed for patients receiving ISIS 420915 by summing the dose administered between **Day 1 of ISIS 420915** and the last dose date in the parent study for patients who are not enrolled in the OLE study or the last dose date in the OLE study for patients who are enrolled in the OLE study. Total dose will be summarized in milligrams as part of longitudinal safety analysis.

• Duration of drug exposure in OLE study (days) will be derived as the difference in days between the date of the last dose of ISIS 420915 in OLE study and **CS3 Study Day 1** plus one.

The total dose of study drug during the treatment period for the OLE study will be computed for patients receiving ISIS 420915 in the OLE study by summing the dose assigned between **CS3 Study Day 1** and the EOT date or date of early termination in OLE study. Total dose will be summarized in milligrams.

3.2.1.1.6 *Immunogenicity (IM):*

- For subjects with negative IM status in the parent study, the onset (T_{first}) of anti-ISIS 420915
 antibodies in OLE study will be derived as difference in days between the date when first
 immunogenicity sample becomes confirmed positive (i.e., positive sample IM status) in OLE study
 and Day 1 of ISIS 420915 plus one.
- For subjects with positive IM status in the parent study, the onset (T_{first}) of anti-ISIS 420915 antibodies in the parent study will be used as the onset of the OLE study.

3.2.1.1.7 BMI and mBMI:

• Body mass index (BMI) will be computed using the formula:

BMI = (weight in kilograms) / [height in cm / 100]²

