3.2.2 Patient Populations Analyzed

The following analysis populations are defined for this present OLE study:

- Screened patients will be defined as patients who signed an informed consent form.
- Enrolled patients will be defined as patients who signed an informed consent form and were not screen failures.
- The FAS will include all enrolled patients who received at least 1 injection of ISIS420915 in the
 OLE study and who have at least one post-baseline efficacy assessment for the mNIS+7 score or
 Norfolk QOL-DN questionnaire total score collected after CS3 Study Day 1 in this OLE study. This
 will be the primary population for analysis of efficacy and PD outcomes.
- The Safety Set (SS) will include all enrolled patients who received at least 1 injection of ISIS
 420915 in the OLE study. This population will beused for analyses of all safety measures
 collected in this OLE study. Results will be summarized under the treatment which the patients
 received in the parent study.
- The Longitudinal Safety Set (LSS): will include all patients who received at least 1 injection of ISIS 420915 in the parent study. This population will beused for the longitudinal safety analysis for either the parent study or this OLE study. Results will besummarized under the treatment which the patients received in the parent study. Note that this population will include patients who receive ISIS 420915 in the parent study but did not enter this OLE. It does not include patients who took placebo in CS2.
- The PPS will include the subset of the Full Analysis Set that have received at least 70% of the prescribed doses of ISIS 420915 in this OLE study and that have no significant protocol deviations in the OLE study that would be expected to affect efficacy assessments. Prescribed doses of ISIS420915 mentioned above is defined as the total assigned dose in mg from the Week 1 to the last dose within this study up to week 156 (first three years), i.e. 300mg*156 doses= 46800mg. Patients in FAS of this OLE study but excluded from PPS in the parent study will be excluded from the PPS in this OLE study as well. This will be a secondary population for

efficacy and PD analyses. The detailed criteria and definitions for major protocol violations will be specified. Results will be summarized under the treatment which the patients received in the parent study.

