Missing/partial dates (month and year) for the duration of disease from diagnosis for FAP/FAC and duration from onset of symptoms for FAP/FAC will be imputed as follows: since CRF only collects year and month for FAP and FAC Diagnosis and onset of symptoms, for calculating the duration, a day of 15th will be used if only day is missing. JUL01 will be used if both day and month are missing. If the imputed date is after the date of informed consented at CS2, use the informed consented at CS2 as the imputed date. Calculate as following

- (a) Duration (month) = number of month (date of informed consented at CS3- date of FAP or FAC diagnosis + 1)
- (b) Duration (month) = number of month (date of informed consented at CS3- date of onset of FAP or FAC symptoms + 1)

Exposure to Study Drug in OLE study will be summarized by treatment group of the parent study for the SS by durations of drug exposure in OLE study (days), total number of dose received, and total dose administered (in milligrams). Across all visits, number of subjects with dose pauses and reasons for dose pause will be tabulated. A listing presenting for each subject the number of dose reductions (frequency of administered dose < protocol defined dose, i.e. 300 mg) and missed doses (injection not givens) will be provided. Doses that were not given because the patient discontinued will not be summarized.

Overall drug exposure from the start of the parent study to the end of the OLE study will be summarized for patients who took ISIS 420915 in the parent study, i.e. LSS.

Medical history and baseline physical examination findings collected in the OLE study will be listed depending on the data availability.

Medications will be coded using WHO Drug Dictionary. The final version used will be designated in the clinical study report. Concomitant medications used will be summarized by treatment group for the SS and the CM-ECHO Set.

All medications including concomitant medications will also be listed in a by patient listing. In the listing, medications which are started before the **CS3 Study Day 1** will be marked.

Patients with any anti-platelet or anti-coagulant medication taken at any time during this study will be presented in a listing.

A concomitant medication is defined as any medication taken whilst investigational product is being taken in this study.

If a partial date is recorded in the case report form, the following convention will be used to assign the medication:

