9.1 Analyses Removed from Final Analyses

Per protocol set (PPS) flag will not created in final ADaM dataset and Efficacy and PD analysis based on PPS will not be performed.

Efficacy analysese by subgroup will not be performed.

The degree of progression for mNIS+7 and Norfolk (specified in section 3.4.2.1) will not be performed

The proportion of patients with percentage decrease from either the parent study baseline or the OLE study baseline in plasma transthyretin (TTR) \geq 60% (specified in section 3.5) will not be performed.

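### The SAP's OLE total-dose rule sums doses assigned, but the exposure summary it feeds reports dose administered

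*Combined protocol and SAP*

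**What the plan says.** SAP 3.2.1.1.5 contains two total-dose rules, both in milligrams.

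- **Cross-study rule.** The total is obtained "by summing the dose administered between" Day 1 of ISIS 420915 and the last dose date, which is the last OLE dose for anyone who entered the OLE. It is reported as part of the longitudinal safety analysis.
- **OLE rule.** The total is obtained "in the OLE study by summing the dose assigned between" two dates. The sum starts at CS3 Study Day 1, and its end point is given as "the EOT date or date of early termination in OLE study".

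The OLE duration rule immediately above the second of these stops at the last OLE dose.

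SAP 3.2.3 specifies the OLE exposure summary on the Safety Set. Besides duration, it lists "total number of dose received, and total dose administered (in milligrams"). Protocol 10.6.2 sets the requirement that the SAP implements: "Treatment duration and amount of ISIS 420915 received (including duration and amount in the parent study) will be summarized by treatment group".

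The word *assigned* has one worked use elsewhere in the SAP. In the Per-Protocol Set definition (SAP 3.2.2), prescribed doses are "defined as the total assigned dose in mg from the Week 1 to the last dose within this study", up to Week 156, and are put at 46,800 mg.

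**The concern.** The derivation and the label on the output describe different quantities. A dose that was due but not injected belongs in an assigned total and not in an administered one. The two also differ in end point: a termination date in one case, the last injection in the other.

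The plan expects such gaps. SAP 3.2.3 tabulates dose pauses and lists missed and reduced doses. The protocol provides for interruptions for renal findings (8.5.2), for missing platelet results and travel (8.5.4) and for low platelet counts (8.6.3).

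The primary objective is the safety and tolerability of extended dosing, so the exposure table should show what patients received. Under the rule as written, a patient's row could show a dose count and an mg total that do not agree.

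**Working it through.** **1. Reproduce the plan's figure.** Weekly dose 300 mg and 156 doses (SAP 3.2.2): 300 × 156 = 46,800 mg. This matches the stated assigned total. For the maximum OLE treatment period of 260 weeks (protocol 3.4.2): 300 × 260 = 78,000 mg.

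**2. Compare the wording.**

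| Place | Quantity | End point |
|---|---|---|
| SAP 3.2.1.1.5, cross-study total | administered | last dose |
| SAP 3.2.1.1.5, OLE total | assigned | end of treatment or early termination |
| SAP 3.2.1.1.5, OLE duration | days | last OLE dose |
| SAP 3.2.3, OLE summary | administered | not stated |
| Protocol 10.6.2 | received | not stated |

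Only the OLE total uses *assigned*, and only that row runs to a termination date. SAP section 9, which lists the analyses removed from and added to the final analysis, does not revise it.

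**3. Effect of missed doses.** Take N assigned weekly doses of 300 mg, of which k are missed but still count as assigned. The assigned total is 300N and the administered total is 300(N − k), so the overstatement is N/(N − k) − 1. The values of k are assumptions; the documents give no rate.

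| N | k | Assigned (mg) | Administered (mg) | Overstatement |
|---|---|---|---|---|
| 156 | 4 | 46,800 | 152 × 300 = 45,600 | 2.6% |
| 156 | 12 | 46,800 | 144 × 300 = 43,200 | 8.3% |
| 260 | 4 | 78,000 | 256 × 300 = 76,800 | 1.6% |
| 260 | 12 | 78,000 | 248 × 300 = 74,400 | 4.8% |

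With k = 0 the two totals agree. In the second row the summary would show 144 doses received beside 46,800 mg labelled as administered, although 144 doses of 300 mg make 43,200 mg.

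**4. Held and reduced doses.** These add to the excess only if *assigned* means the prescribed 300 mg weekly, as in the Per-Protocol Set definition. A hold required by the protocol could equally be read as no dose assigned. A reduced regimen carried over from the parent study (SAP 2.2) could be read as the assigned dose.

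**5. End date.** The SAP does not say whether the early-termination date is the termination visit or the end of dosing. Protocol 8.8 places the termination visit ideally within 14 days of the last dose, which is a target and not a limit. SAP 3.2.3 also says that doses not given because of discontinuation are not summarised. The end-date effect may therefore be nil, and I put no figure on it.

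**6. Parent-study placebo patients.** SAP 3.2.1.1.1 sets their Day 1 of ISIS 420915 at their first OLE dose. Both rules in SAP 3.2.1.1.5 then cover the same course of treatment, one by dose administered and one by dose assigned. Only the assigned version is summarised for them, because the longitudinal display is on the Longitudinal Safety Set: "It does not include patients who took placebo in CS2".

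**The case against.** The best reply is that *assigned* is a slip of one word. SAP 3.2.3 names the output plainly, protocol 10.6.2 agrees with it, and the neighbouring rule already sums dose administered, so a programmer building the table has a clear target. The one worked use of *assigned* as prescribed dose sits in a definition that the final analysis abandons ("Per protocol set (PPS) flag will not created in final ADaM dataset"), and it runs to the last dose rather than to a termination date. This shows that the intention is probably dose administered. It does not settle the matter: SAP 3.2.3 gives no derivation, and the only rule written specifically for the OLE total says otherwise.

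Four stronger readings are tempting, and the documents do not support them.

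- **Every patient who missed or paused a dose would have an inflated total.** This is too broad, because a held dose may never have been assigned.
- **The OLE rule gives the only mg total defined for parent-study placebo patients.** The cross-study rule also defines one for them; what they lack is its display.
- **Early terminators gain a dose or two.** That depends on an undefined termination date and a 14-day target.
- **Safety conclusions are distorted.** Adverse events are grouped by duration of exposure and number of doses (SAP 3.3.2.6 and 3.3.2.7), and no planned safety analysis in this SAP uses OLE mg as a denominator or grouping variable.

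A reader could also detect a discrepancy by setting mg against doses received and the missed-dose listing. That limits the harm but does not make the rule right.

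**Conclusion.** The inconsistency is real and stands in current text. The OLE rule in SAP 3.2.1.1.5 does not produce the quantity that SAP 3.2.3 reports and protocol 10.6.2 requests. Followed literally, it can overstate the dose given.

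The sizes above rest on assumed counts of 4 to 12 missed doses, 300 mg weekly throughout, and missed injections still counting as assigned. They illustrate the arithmetic and do not estimate what happened in the study. The error is zero for a patient with no missed, held or reduced doses whose total stops at the last dose, and zero for everyone if the programmer follows SAP 3.2.3.

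The consequence is limited to the descriptive OLE mg summary. Duration, number of doses received and the longitudinal mg total are unaffected. SAP 9.2.2 brings in some outputs from an integrated safety SAP that is not among the documents, so those could not be checked. Severity: minor. Confidence is high for the mismatch in wording, but not for any particular amount of overstatement.

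**What to change.** In SAP 3.2.1.1.5, replace the OLE rule with: *summing the dose administered (missed or held injections = 0 mg) from CS3 Study Day 1 to the last dose date in the OLE study*. This aligns it with SAP 3.2.3, protocol 10.6.2, the OLE duration rule and the cross-study rule in the same section. It changes only the exposure calculation and no dosing rule.

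The cost is one sentence and one derivation. The cross-study rule already needs administered doses through the end of the OLE, and SAP 3.2.3 already needs a count of doses received, so no new data are called for. Totals do not change for patients who received every assigned dose in full and whose sum already ended at the last dose.

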3.2.1.2 Scoring of Assessment Instruments

mNIS+7

The mNIS+7 consists of two composite scores: the NIS composite score (maximum of 244 points) and the modified +7 composite score (maximum of 102.32 points).

NIS

The NIS composite score consists of 4 components:

- Cranial Nerves (NIS-C), maximum 40 points
- Muscle Weakness (NIS-W), maximum 152 points
- Reflexes (NIS-R), maximum 20 points
- Sensation (NIS-S), maximum 32 points.

Questions that make up each composite are listed in the table below.

NIS composite	Question number
Cranial Nerves	1-5
Muscle Weakness	6-24
Reflexes	25-29
Sensation	30-37

Note that each question is separately assessed for the right and left side of the body, meaning that questionnaire is comprised of 74 subcomponents (37 for the left side, and 37 for the right side).

Modified +7

The modified +7 composite score consists of 4 components:

- 1 component for autonomic nerve assessment:
 - Heart Rate to Deep Breathing (HRDB), minimum -3.72 points, maximum 3.72 points,
- 1 component for the nerve conduction assessment of the lower and upper limbs:
 - \circ Nerve Conduction Tests (Σ 5 NC), maximum 18.6 points from 5 subcomponents (PMAK, TMAK, UMAE, USAW, SSAB) with minimum -3.72 points and maximum +3.72 points each,
- 2 components for the sensory nerve assessment:
 - o Touch-Pressure (TP), maximum 40 points
 - Heat-Pain (HP), maximum 40 points.
 NOTE: Testing for both TP and HP is done at up to 10 sites on one side of the body. To obtain the full body score for TP and HP, the summation scores from all 10 anatomical sites

is multiplied by 2 (only one side of the body is tested as FAP is symmetrical neuropathy, identical results are assumed for the other side).

Component	Data entry convention /Comment	Pre-processingstep
Heart Rate Deep Breathing	If HRDB could not be measured due to pacemaker or arrhythmia, MC Core checked either the box "no reliable data to due pacemaker" or "no reliable measure points due to arrhythmia," and left the HRDB score as blank in the BioClinica database	None
	If HRDB was not measured in error or missing for other reasons, MC Core entered a "-9" into the BioClinica database	Set "-9" to missing
	Transform normaldeviate score so that larger values coincide with worse outcomes	Multiply subcomponent score by "-1"
Nerve conduction test	If the nerve attribute was not tested in error, MCCore entered a "-9" into the BioClinica database	Set "-9" to missing
	For all 5 subcomponent (SSAB, USAW, UMAE, PMAK, TMAK) transform subcomponent normal deviate score so that larger values coincide with worse outcomes	Multiply each subcomponent score by "-1"
Touch Pressure	If an anatomical site was assessed, , MC Core entered a "O", "1" or "2" into the BioClinica database	None
	If an anatomicalsite was skipped because it was assumed to be< 95%, MC Core left the field blank in the BioClinica database (the last assessed more distalanatomical site has a "O" entered)	Set blank field to "O"
	If an anatomicalsite was not tested in error, MC Core entered a "-9" into the BioClinica database	Set "-9" to missing
Heat Pain	If an anatomicalsite was assessed, MC Core entered a "O", "1" or "2" into the BioClinica database	None
	If an anatomical site was skipped because it was assumed to be< 95%, MC Core left the field blank in the BioClinica database (the last assessed more distalanatomical site has a "O" entered)	Set blank field to "O"

If an anatomical site was not tested in error, MC Core entered a "-9" into the BioClinica database	Set "-9" to missing
--	---------------------

Additionally, for Heat Pain and Touch Pressure, the composite scores are calculated by multiplying the sum of the 10 averaged subcomponent scores (defined below) by 2.

NIS+7

The NIS+7 consists of two composite scores: the NIS composite score (above) and the +7 composite score (maximum of 26.04 points).

+7

The +7 composite score consists of 3 components:

- 1 component for autonomic nerve assessment:
 - Heart Rate to Deep Breathing (same as modified +7), minimum -3.72 points, maximum 3.72 points,
- 1 component for the peripheral nerve assessment of the lower limb:
 - Nerve Conduction Tests (LS NC nds), maximum 18.6 points from 5 subcomponents (PMAK, PMCVK, PMLA, TMLA, SSAB) with minimum -3.72 points and maximum +3.72 points each. Please note that 3 of the subcomponents used in +7 (PMCVK, PMLA, TMLA) are different from 3 of the subcomponents used in modified +7 (TMAK, UMAE, USAW).
- 1 component for the sensory nerve assessment
 - o Vibration Detection Threshold (VDT), minimum -3.72 points, maximum 3.72 points.

Due to the testing algorithm and the MC Core data entry conventions, raw+ 7 data need to undergo a pre-processing step before the scores can be derived. The different pre-processing steps are summarized in the table below.

Component Data entry convention /Comment		Pre-processing step
Heart Rate Deep Breathing	If HRDB could not be measured due to pacemaker or arrhythmia, MC Corechecked either the box "no reliable data to due pacemaker" or "no reliable measure points due to arrhythmia," and left the HRDB score as blank in the BioClinica database	None
	If HRDB was not measured in error or missing for other reasons, MC Core entered a "-9" into the BioClinica database	Set "-9" to missing
	Transform normal deviate score so that larger valuescoincide with worse outcomes	Multiply subcomponent score by "-1"

Nerve conduction test	If the nerve attribute was not tested in error, MC Core entered a "-9" into the BioClinica database	Set "-9" to missing
	For PMCVK, PMLA, TMLA, if the attribute could not be estimated/ measured due to an amplitude (CMAPS) of O in the fibular or tibial nerve, MC Core left the field blank in the BioClinica database	See imputation method for group B below
	For PMAK, PMCVK, SSAB, transform normal deviate subcomponent score so that larger valuescoincide with worse outcomes	Multiply subcomponent score by "-1"
Vibration Detection	If the vibration test was not tested in error, MC Core entered a "-9" into the BioClinica database	Set "-9" to missing

Norfolk QOL-DN

The Norfolk QOL-DN (version: 2003) consists of one composite score (Total QOL) and five subdomain scores (physical functioning/large fiber neuropathy, activities of daily living, symptoms, small fiber neuropathy, and autonomic neuropathy). The scoring of the Norfolk QOL-DN will be conducted according to the scoring manual developed at the Eastern Virginia Medical School, and is summarized below.

Questions that make up each domain are listed in the table below

Norfolk QOL-DN Domain	Question number
physical functioning/large fiber neuropathy	8, 11, 13-15, 24, 27-35
activities of daily living	12,22,23,25,26
symptoms	1-7, 9
small fiber neuropathy	10, 16, 17, 18
autonomic neuropathy	19,20,21

All symptoms (Questions 1 to 7) are a simple inventory of symptoms of neuropathy. Each of these questions are assessed for the feet, legs, hands and arms, with presence of a symptom scored as a 1 and absence as a 0. The Question Score is calculated by summing the scores for the individual sites for the Question, with the Question Score ranging from O (no symptoms) to 4 (symptoms in the feet, legs, hands, and arms). The other Questions, except Questions 31 and 32, are scaled on a 5 point Likert scale, ranging from O ("Not a problem") to 4 ("Severe Problem"). In Question 31, "Good" is scored as 0, "Very Good" is scored as -1, "Excellent" is scored as -2, "Fair" is scored as 1, and "Poor"

is scored as 2. In Question 32, "About the same" is scored a 0, "Somewhat better" is scored a -1, "Much better" is scored a -2, "Somewhat worse" is scored a 1, and "Much worse" is scored a 2.

SF-36

The SF-36 (version: 2) consists of two composite scores, the Physical Component Summary score and the Mental Component Summary score, as well as eight domain scores (physical function, role-physical, bodily pain, general health, vitality, social functioning, role-emotional, and mental health). The scoring of the SF-36 will be conducted using Quality Metrics Certified Scoring Software v 4.5.

NSC

The NSC questionnaire (version: 04Jan2009) consists of one total score and five domains (muscle weakness, sensory (hypo/loss of sensation), sensory (paresthesia, hyper sensation), autonomic (gastro intestinal (GI) and urinary incontinence), and autonomic (non-GI/non-urinary incontinence). The muscle weakness domain is divided into four sub-domains (head and neck, chest, upper limbs, and lower limbs). The scoring of the NSC questionnaire is described in the Appendix 2 Scoring of Assessment Instruments.

